3.4.6 Breaking the Blind

A participant or participants may be unblinded in the event of an SAE or other severe event, or if there is a medical emergency requiring the identity of the product to be known to

properly treat a participant. If a participant becomes seriously ill or pregnant during the study, the blind will be broken if knowledge of the administered vaccine will affect that participant's dosing options. In the event of a medical emergency requiring identification of the vaccine administered to an individual participant, the investigator will make every attempt to contact the Sponsor medical lead to explain the need for opening the code within 24 hours of opening the code. The investigator will be responsible for documenting the time, date, reason for the code break, and the names of the personnel involved.

In addition to the aforementioned situations where the blind may be broken, the data will also be unblinded to a statistical team at specified time points for interim analyses as outlined in Section 3.6.8.

3.4.7 Dosing Compliance

All doses of vaccine will be administered at the study site under direct observation of unblinded pharmacy personnel and appropriately recorded (date and time) in the eCRF. Unblinded pharmacy personnel will confirm that the participant has received the entire dose of vaccine. If a participant does not receive vaccine or does not receive all of the planned doses, the reason for the missed dose will be recorded.

Participants who miss the second vaccination due to noncompliance with the visit schedule and not due to a cohort pause will still be required to follow the original visit and testing schedule as described in the protocol. Unless consent is withdrawn, a participant who discontinues from receiving the second dose of study vaccine will remain in the study and complete all safety and immunogenicity procedures required through 1 month after the last vaccination received per the Schedule of Events (i.e., up to Day 29 for subjects receiving only the first dose of vaccine). Subjects will then enter the 12-month Long-Term Follow-up Phase per the Schedule of Events (Table 5).

Subjects will enter the Long-Term Follow-up Phase starting at Month 3 and will complete protocol-specified procedures, including further blood sampling for immunogenicity at Month 7 and Month 13 (Table 5).

The study site is responsible for ensuring participants comply with the study windows allowed. If a participant misses a visit, every effort should be made to contact the participant and complete a visit within the defined visit window. If a participant exceeds their

post-vaccination visit in excess of 28 days from the scheduled visit or misses a vaccination schedule by more than 28 days (i.e., 28 days beyond the scheduled time of vaccination), then that visit will be classified as a missed visit and the participant will continue with subsequent study visits. All safety requirements of the missed visit will be captured and included in the subsequent visit (e.g., clinical laboratory testing, diary card review for reactogenicity, immune testing, as applicable).

3.4.8 Prior and Concomitant Medications

3.4.8.1 Prior Medications and Therapies

Information about prior medications (including any prescription or over-the-counter medications, vaccines, or blood products) taken by the participant within the 30 days before providing informed consent (or as designated in the inclusion/exclusion requirements) will be recorded in the participant's eCRF.

3.4.8.2 Concomitant Medications and Therapies

Concomitant medications include all medications (including vaccinations received outside of the study) that the participant takes from the time of signing the informed consent form (ICF) through the follow-up visit at Month 13. At each study visit, the site personnel should question the participant about concomitant medications use, including any vaccinations received, and record use in the eCRF.

The use of the following concomitant medications and/or vaccines will not require withdrawal of the participant from the study but may determine a participant's evaluability in the per-protocol analysis (analysis sets are described in Section 3.6.5):

- Any investigational or nonregistered product (drug or vaccine) other than the study vaccine used during the study period.
- Immunosuppressants or other immune-modifying drugs administered chronically (i.e., more than 14 days in total) during the study period. For corticosteroids, this will mean that prednisone ≥ 20 mg/day or the equivalent is not permitted. Inhaled, nasal, and topical steroids are allowed.

- Long-acting immune-modifying drugs administered at any time during the study period (e.g., infliximab).
- A vaccine not foreseen by the study protocol administered during the period from 30 days before through 30 days after each study vaccination, except for any licensed influenza vaccine that was administered ≥ 15 days before or after any study vaccination.
- Immunoglobulins and/or any blood products administered during the study period.
- Any hepatotoxic drugs administered chronically (i.e., more than 14 days in total) (Appendix 4).
- Analgesics/antipyretics may be used post-vaccination for symptomatic relief of reactogenicity symptoms.

Concomitant medications (including vaccinations) will be coded using the WHO Drug Dictionary. If a participant takes a prohibited drug therapy, the investigator and the CRO medical monitor will make a joint decision about continuing or withholding further vaccination of the participant based on the time the medication was administered, the drug's pharmacology and pharmacokinetics, and whether use of the medication will compromise the participant's safety or interpretation of the data. It is the investigator's responsibility to ensure that details regarding the concomitant medications are adequately recorded in the eCRF.

3.5 Study Procedures

Before performing any study procedures, all potential participants will sign an ICF (as detailed in Section 4.3). Participants will undergo study procedures at the time points specified in the Schedule of Events (Table 5).

A participant also can be seen for an unscheduled visit at any time during the study. An unscheduled visit may be prompted by reactogenicity issues, new or ongoing AEs, or abnormal clinical laboratory test results. The site also has the discretion to make reminder telephone calls or send text messages to inform the participant about visits, request further laboratory assessments, review diary card content requirements, or follow up on ongoing or outstanding issues.

3.5.1 Safety Telephone Calls

A safety telephone call is a telephone call made to the participant by trained site personnel. This call will follow a script, which will facilitate the collection of relevant safety information. The participant will be interviewed according to the script, about occurrence of AEs, MAAEs, SAEs, AESI, or AEs leading to study withdrawal and concomitant medications associated with those events will be collected.

Additionally, in the Vaccination Phase of the study, the site will telephone the participant for safety monitoring on each of the 2 days after study vaccination (i.e., Day 2 and Day 3 after the first vaccination and Day 30 and Day 31 after the second vaccination). The purpose of this safety telephone call is to identify any rash or Grade 3 local and systemic reactogenicity AEs (solicited AEs) that may occur within 48 hours after study vaccination and to ensure that they are recorded in the eCRF and reported to the medical monitor in a timely manner.

The timing of the safety telephone calls is provided in Table 5.

All safety information described by the participant must be documented in source documents and not documented on the script used for the safety telephone contact.

3.5.2 Completion of Diary Card

At each vaccination visit (Day 1 and Day 29), study staff will provide a diary card to participants and training on its proper use. The participant will use the diary card for recording AE information; this information will be subject to potential change based on further questioning and/or follow-up by study staff.

Each participant will be instructed to complete the diary card to including the following:

- Solicited local and systemic reactogenicity AEs, as defined in Section 3.5.6, that
 occur on the day of each vaccine administration and during the 7 days after vaccine
 administration, with appropriate documentation to allow severity scoring by the
 investigator.
- Daily oral body temperature measurement should be performed at approximately the same time each day using the thermometer provided by the study site. If body

temperature is taken more than once in a given day, only the highest temperature reading should be recorded.

- Measurement, as applicable, for solicited local AEs; the size measurements will be performed using the ruler provided by the study site.
- All medications (excluding vitamins and minerals) taken on the day of each vaccine administration and during the 28 days after vaccine administration.
- Any unsolicited AE (Section 3.5.7) during the 28 days after each vaccine administration

During clinic visits, study staff will review the diary card information regarding solicited and unsolicited AEs, body temperature, and concomitant medications. This information will be recorded in the participant's source documents and the eCRF.

Diary cards will be the only source documents allowed for solicited systemic and local AEs (including body temperature measurements). The following additional rules apply to documentation of safety information collected using Diary Cards:

- No corrections or additions to the Diary Card will be allowed after it is delivered to the site.
- Any blank or illegible fields on the Diary Card must be described as missing data.
- The site staff must enter all readable entries in the Diary Cards into the eCRF.
- Any new safety information reported during the site visit (including a solicited reaction) must not be written into the Diary Card and must be described in the source documents as verbally reported event. Any adverse reaction reported in this manner must be described as an unsolicited reaction and therefore entered on the adverse event eCRF.

Any unreturned Diary Cards will be requested from the subject through telephone call(s) or other suitable method.

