3.5.7.1.1 Definitions

An AE is defined as any untoward medical occurrence associated with the use of a drug in humans, whether or not considered drug related. Participants will be instructed to record any AEs (solicited or unsolicited) in the diary card.

A treatment-emergent AE (TEAE) is defined as any event not present before exposure to vaccine or any event already present that worsens in intensity or frequency after exposure.

A suspected adverse reaction is any AE for which there is a reasonable possibility that the vaccine caused the AE. For the purposes of investigational new drug safety reporting, "reasonable possibility" means that there is evidence to suggest a causal relationship between the vaccine and the AE. A suspected adverse reaction implies a lesser degree of certainty about causality than adverse reaction, which means any AE caused by a vaccine. Adverse reactions are a subset of all suspected adverse reactions for which there are reasons to conclude that the drug caused the event.

An unsolicited AE is any AE reported by the participant that is either (1) not specified as a solicited AE in the protocol or (2) specified as a solicited AE in the protocol, but its onset occurs outside of the protocol-defined post-vaccination period for reporting solicited AEs (i.e., for the 7 days after each vaccination; Section 3.5.6 for additional information on solicited safety measures).

An AE or suspected adverse reaction is considered "unexpected" if it is not listed in the IB or is not listed at the specificity or severity that has been observed with the vaccine being tested or, if an IB is not required or available, it is not consistent with the risk information described in the general investigational plan or elsewhere in the current application. For example, under this definition, hepatic necrosis would be unexpected (by virtue of greater severity) if the IB referred only to elevated hepatic enzymes or hepatitis. Similarly, cerebral thromboembolism and cerebral vasculitis would be unexpected (by virtue of greater specificity) if the IB listed only cerebral vascular accidents. "Unexpected," as used in this definition, also refers to AEs or suspected adverse reactions that are mentioned in the IB as occurring with a class of drugs or as anticipated from the pharmacological properties of the drug but are not specifically mentioned as occurring with the particular drug under investigation.

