Unsolicited AEs will also be evaluated by the investigator for the coexistence of any of the other following conditions:

• Medically attended AE, defined as an AE that leads to an unscheduled visit to a healthcare practitioner

Any solicited AE (Section 3.5.6) that meets any of the following criteria must be entered as an AE in the eCRF:

- Solicited local or systemic AE leading to the participant withdrawing from the study or the participant being withdrawn from the study by the investigator
- Solicited local or systemic AE lasting beyond 7 days post-vaccination
- Solicited local or systemic AE that leads to participant withdrawal from vaccine
- Solicited local or systemic AE that otherwise meets the definition of an SAE
- Laboratory test result or vital sign measurements with a toxicity score of Grade 3 or greater

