7.6.2 Adverse Events

An unsolicited AE is any AE reported by the participant that is either (1) not specified as a solicited AE in the protocol or (2) specified as a solicited AR in the protocol, but its onset occurs outside of the protocol-defined post vaccination period for reporting solicited AEs (ie, for the 7 days after each vaccination). A solicited ARs that meet the criteria for an SAE will also be recorded as an unsolicited AE.

A treatment-emergent AE (TEAE) is defined as any AE not present before exposure to vaccine or any AE already present that worsens in intensity or frequency after exposure. Only TEAEs are collected in this study.

An MAAE is defined as an AE that leads to an unscheduled visit to a healthcare practitioner.

Unsolicited AEs will be coded by PT and SOC using MedDRA and summarized by treatment, vaccination (first or second) and overall. Summaries for each vaccination will include AEs that occur during the 28 -day follow-up period after each vaccine.

All summaries of unsolicited AEs will present number and percentage of subjects in each category. For those summaries presented by PT, the preferred terms will be sorted in descending order of frequency within the mRNA-1893 treatment group.

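### Solicited reactions first reported at a site visit are relabelled as unsolicited, against the definition of an unsolicited AE, and the SAP does not say where they count

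*Protocol*

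**What the plan says.** Protocol 3.5.2 fixes the source of the solicited data: "Diary cards will be the only source documents allowed for solicited systemic and local AEs (including body temperature measurements"). It allows no corrections or additions once the card has reached the site and treats blank or illegible fields as missing. It then deals with safety information that first comes up when the participant attends in person ("including a solicited reaction) must not be written into the Diary Card and must be described in the source documents as verbally reported event"), and concludes: "Any adverse reaction reported in this manner must be described as an unsolicited reaction and therefore entered on the adverse event eCRF".

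The definition of an unsolicited AE runs on a different principle. Apart from terms that are not on the solicited list, it admits only an event "specified as a solicited AE in the protocol, but its onset occurs outside of the protocol-defined post-vaccination period for reporting solicited AEs" (Protocol 3.5.7.1.1; the Protocol glossary agrees). SAP 7.6.2 repeats the rule: "specified as a solicited AR in the protocol, but its onset occurs outside of the protocol-defined post vaccination period for reporting solicited AEs". How the event was reported plays no part in either text.

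Two further places say when a solicited event also goes on the AE form. Protocol 3.5.7.1.1 introduces its list with "Any solicited AE (Section 3.5.6) that meets any of the following criteria must be entered as an AE in the eCRF". The list covers withdrawal from the study or from vaccine, duration beyond 7 days, seriousness, and Grade 3 or higher laboratory or vital-sign results. SAP 7.6.1 has nearly the same list. SAP 7.6.2 adds one exception: "A solicited ARs that meet the criteria for an SAE will also be recorded as an unsolicited AE". Verbal reporting appears in none of these, and SAP Section 8, which records changes from the protocol, does not mention it.

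**The concern.** The first two primary endpoints are the frequency and grade of solicited reactions over 7 days and of unsolicited AEs over 28 days. The label decides which of the two an event enters. One section assigns the label by reporting route and another by term and onset date, so the same event gets two answers.

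The direction of the error in the solicited table is predictable. The reaction is known to the site but cannot enter the table, while the participant is usually still in the denominator. For that event, a known reactor is tabulated as a non-reactor. In a first-in-human dose-ranging study with 24 vaccinees per dose level, one or two such participants can visibly change a reactogenicity rate. The unsolicited table gains events that it is not defined to contain. Pause rules 4 to 6 in Protocol 3.4.2.2 also divide events by these labels.

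**Working it through.** **1. The plan's own figure.** Protocol 3.6.4 and SAP 5.2 give the probability of seeing at least one participant with an AE among 24 vaccinees. The formula is 1 − (1 − p)^24.
- p = 10%: 1 − 0.90^24 = 0.920 (stated 92%).
- p = 5%: 1 − 0.95^24 = 0.708 (stated 70.8%).

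Both reproduce and neither is in dispute. They confirm 24 as the number per dose level.

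**2. One case traced through the rules.** Suppose a participant records injection-site pain on the card but leaves out fatigue that began on Day 3, hands the card in at Day 8, and mentions the fatigue to staff at that visit.
- *Solicited numerator (Protocol 3.5.2):* the card cannot be amended and is the only permitted source, so the fatigue is not counted.
- *Solicited denominator (SAP 6.1.3):* contributing any solicited data is enough to be in the Solicited Safety Set, so the pain entry keeps the participant in. Under SAP 7.1, percentages use everyone in the set unless otherwise specified.
- *Unsolicited table, by the site's label:* the fatigue is on the AE form as unsolicited and is counted under SAP 7.6.2.1 to 7.6.2.3.
- *Unsolicited table, by the SAP definition:* fatigue is on the solicited list, so the first limb fails. Onset is inside the window, so the second limb fails. A programmer who used the definition as a filter would exclude it.

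Followed as written, the event moves from one primary endpoint to the other. With the definition applied as a filter, it appears in neither.

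**3. Size.** The documents give no frequency for such reports, so the number of participants k is an assumption. The shift in a dose-level rate is k/24:
- k = 1: 4.2 percentage points
- k = 2: 8.3 points
- k = 3: 12.5 points

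Pooled placebo is also 4 × 6 = 24, so the same steps apply there. The solicited rate falls by this amount. The unsolicited rate for that term rises by the same amount if the participant has no other unsolicited record of the term.

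**4. Effect on detection.** Let m be the assumed share of reacting participants known only from a site-visit report. The chance that the solicited table shows at least one of 24 is 1 − (1 − p(1 − m))^24.

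| True incidence p | m = 0 | m = 10% | m = 20% | m = 30% |
|---|---|---|---|---|
| 10% | 92.0% | 89.6% | 86.5% | 82.5% |
| 5% | 70.8% | 66.9% | 62.5% | 57.5% |

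**5. Pause rules (Protocol Table 3).** Rules 4 and 5 count Grade 3 solicited events lasting more than 24 hours within the 7-day period, and rule 5 adds a causality condition. Rule 6 counts Grade 3 or higher unsolicited events with a causality condition and no duration condition. Relabelling an event therefore changes the conditions under which it counts.

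**The case against.** The strongest reply is that nothing is lost. Protocol 3.5.2 gives the event a home on the AE form, the SAP tabulates all unsolicited TEAEs, and no SAP text tells a programmer to remove solicited terms with in-window onset. The SAP already accepts some solicited terms on the AE form. Its precedence clause in Section 2 concerns statistical methods, not data capture. This stands: a reader might infer that the event disappears, but on a literal reading it is moved. Loss from both tables needs a filtering step that the SAP does not order, although its own definition would invite one.

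A reader might also infer that the safety telephone calls feed the problem, since Protocol 3.5.1 says: "The purpose of this safety telephone call is to identify any rash or Grade 3 local and systemic reactogenicity AEs (solicited AEs"). The documents do not support this. The relabelling rule covers information given at a site visit. The calls have their own instruction to record in the eCRF, and footnote m of the Schedule of Events has staff remind participants to keep the card current. A reaction mentioned on Day 2 or 3 can still be written down before Day 8.

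Nor is the solicited rate understated by every blank or incomplete card. A participant with no solicited data is outside the Solicited Safety Set altogether. A blank field causes bias only if a reaction occurred and was not written down, and that under-recording would exist without this rule. What the rule adds is that a reaction the site does know about stays out of the solicited table.

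Diary-only sourcing is probably deliberate and is defensible, because prospective recording and later recall are not equivalent. On pauses, a relabelled event can still count under rule 6, and those overseeing safety may ask for a pause on any concern. That softens the practical effect but does not settle which label applies.

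**Conclusion.** The inconsistency is real and should be corrected. Protocol 3.5.2 classifies by reporting route, the definitions in the protocol and SAP classify by term and onset, and no text connects them. The result is a misclassification between two primary endpoints that lowers the solicited rate, with no SAP rule for the records concerned.

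The effect is confined to in-window reactions that are absent from the card and first reported at a site visit. The 4.2 to 12.5 point range rests on an assumed 1 to 3 such participants among 24, all of whom stay in the denominator. The detection figures rest on an assumed share of 10% to 30%. Neither assumption can be checked against the documents, and the true number could be zero.

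**What to change.** - **Keep the diary-only solicited table** as the planned analysis.
- **SAP 7.6.2:** flag AE-form records that carry a solicited term with onset in the solicited window, and show them in a separate row of the unsolicited summaries. Reactions already on the diary and re-entered because they lasted beyond 7 days should be told apart from those known only from the AE form.
- **SAP 7.6.1:** add a supplementary table of participants with each solicited reaction from either source, counting each participant once.
- **Window for the flag:** use the same window as SAP 7.6.1, once the wordings agree. Protocol 3.5.2 and SAP 6.1.3 run through 7 days after vaccination. Protocol 3.5.6 and SAP 7.6.1 run through 6.
- **Protocol:** reconcile 3.5.2 with 3.5.7.1.1 and the glossary. Reconcile pause rules 4 to 6 with whichever labelling results. No particular pause rule is proposed here.

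The cost is one programming flag, one extra row and one set of supplementary tables, all from data already collected. The drawback is that the either-source table mixes prospective diary entries with recalled events that differ in detail, so it should be labelled supplementary.
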